### **The study population is characterized through the inclusion criteria:**

Criterion no. 1 is included in accordance with Good Pharmacoepidemiology Practices (GPP).

Criterion no. 2 is included in accordance with Good Pharmacovigilance Practice (GVP) and for the purpose of reflecting local clinical practice.

Criterion no. 3 is included to reflect the population for which Sogroya® (somapacitan) is approved.

Criterion no. 4 is included to ensure that adults enrolled in the study are GH deficient and reflect the population for which Sogroya® (somapacitan) is approved and marketed in the respective countries.

### **The study population is characterized through the exclusion criteria:**

Criterion no. 1 is to ensure that a patient only counts once in the data analyses.

Criterion no. 2 serves to protect patient safety and rights.

Criterion no. 3 is to exclude patients with hypersensitive to Sogroya® (somapacitan) or any of its excipients in accordance with the summary of product characteristics (SmPC)

Criterion no.4 is to exclude patients with any evidence of active malignancy. Any pre-existing malignancy should be inactive, and its treatment complete prior to instituting therapy with Sogroya® (somapacitan) in accordance with the SmPC.

Criterion no.5 is to exclude patients with increased risk of mortality, in accordance with the SmPC.

### **9.2.5 Withdrawal criteria**

The patient may withdraw at will at any time.

In case of withdrawal, the physician should attempt to collect any outstanding data. The primary reason (withdrawal of consent, lost to follow up or other) for discontinuation should be specified in the Case Report Form (CRF).

Protocol  
 Study ID: NN8640-4515  
 UTN: U1111-1264-8642  
 EU PAS No: Pending

**CONFIDENTIAL**

Date:  
 Version:  
 Status:  
 Page:

15 February 2022  
 3.0  
 Final  
 21 of 53

**Novo Nordisk**

## 9.2.6 Visit procedures

### 9.2.6.1 Study flow chart

	Section	Baseline	Visits	Follow-Up
Visit		Visit 1	Visit 2, 3, 4 etc	End of Study
PATIENT RELATED INFORMATION AND ASSESSMENTS				
Informed Consent & Demography	10.1 9.2.8.1	X		
In/exclusion Criteria	9.2.2 9.2.3	X		
Body Measurements	9.2.8.2	X	X	X
Tobacco use	9.2.8.4	X	X	X
Medical history / Concomitant illness	9.2.8.5 9.2.8.6	X		
Concomitant medication	9.2.8.7	X	X	X
Dosing and titration	9.2.8.8		X	X
Adverse event	11		X	X
Physical examination	9.2.7.3	X	X	X
Vital Signs	9.2.8.3	X	X	X
ECG	9.2.7.4	X	X	X
Biochemistry	9.2.7.2	X	X	X
Lipid profile	9.2.7.2	X	X	X
Glucose metabolism	9.2.7.2	X	X	X
Body Composition	9.2.7.6	X	X	X
Biomarkers	9.2.7.5	X	X	X
PRO questionnaires	9.2.8.9	X	X	X
Clinical response evaluation	9.2.8.10		X	X
End of study	9.2.6.2			X

### 9.2.6.2 Study visits

Patients should receive treatment and care at their respective clinic in accordance with normal clinical practice. For each clinical visit and clinical patient contact (e.g., phone call etc) the site personnel should enter all available information in the eCRF as specified in the below sections.

The physician should keep a patient enrolment log.

#### Baseline (visit 1)

Relevant data available in the patient's medical record at the time of the baseline visit may be used as baseline data and should be entered in the eCRF after having obtained informed consent. All relevant data necessary for evaluating whether a patient can be enrolled in the study e.g. inclusion/exclusion criteria, see section [9.2.2](#) and [9.2.3](#), must be available prior to enrolling a patient.

Protocol  
 Study ID: NN8640-4515  
 UTN: U1111-1264-8642  
 EU PAS No: Pending

**CONFIDENTIAL**

Date:	15 February 2022	Novo Nordisk
Version:	3.0	
Status:	Final	
Page:	22 of 53	

Relevant data regarding the assessments listed in the flow chart for visit 1 must be entered in the eCRF, if available.

### **Visits 2, 3, 4 etc**

At each contact with the site during the study, the patient should be asked about possible adverse events since the last contact. This may be done by posing a simple question such as “have you experienced any problems since the last contact?”

Relevant data regarding the assessments listed in the flow chart must be entered in the eCRF, if available.

In case a patient contacts the site (phone, virtual etc) during his/her participation in this study all relevant study information, i.e., reported AEs, should be entered in the patient’s medical records and subsequently in the eCRF in accordance with the flowchart.

### **End of study**

This visit will take place no later than the planned study LPLV date.

Relevant data regarding the assessments listed in the flow chart must be entered in the eCRF, if available.

## **9.2.7 Assessments for safety and other clinical parameters**

### **9.2.7.1 Adverse Events**

All AEs, either observed by the physician or reported by the patient following the patient’s enrolment (signing informed consent) into the study and until the end of study for each patient must be recorded and evaluated by the physician. At each contact with the site during the study, the patient should be asked about possible AEs since the last contact. Please refer to section [11](#) for AE definitions, collection, recording, and reporting.

### **9.2.7.2 Local Laboratory**

Blood samples obtained from local laboratory in accordance with normal clinical practice should be recorded in the eCRF if available and may include:

Applicable local laboratory reference ranges must be collected and shared with Novo Nordisk.

- **Biochemistry**

- Creatinine
- High-Sensitive C-Reactive Protein
- Alkaline phosphatase

**Liver function:**

- Aspartate Aminotransferase (AST)
- Alanine Aminotransferase (ALT)
- Gamma-Glutamyltransferase (GGT)
- Bilirubin

Protocol  
Study ID: NN8640-4515  
UTN: U1111-1264-8642  
EU PAS No: Pending

CONFIDENTIAL

Date:  
Version:  
Status:  
Page:

15 February 2022  
3.0  
Final  
23 of 53

Novo Nordisk

- **Lipid profile**

- Total Cholesterol
- Low Density Lipoprotein cholesterol (LDL-Cho)
- High Density Lipoprotein cholesterol (HDL-Cho)
- Triglycerides

- **Glucose metabolism**

Samples should preferably be obtained in a fasting state

- Insulin,
- Blood glucose
- HbA1c

Laboratory data obtained a maximum of 6 months before informed consent have been signed can be used for baseline data if evaluated still to be valid by the physician. If data from more than one previously obtained sample is available, the latest one should be used.

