## 9 Research methods

### 9.1 Study design

This is a non-interventional, multinational multi-centre, prospective, single-treatment arm, observational PASS in AGHD patients. The study will, under routine clinical practice conditions, investigate the long-term safety of Sogroya® (somapacitan), including but not limited to the occurrence of neoplasm, development of type 2 diabetes and medication errors.

Moreover, the titration regimen and clinical parameters of Sogroya® (somapacitan) therapy in AGHD patients will be collected and evaluated, when available as part of routine clinical practice.

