**Novo Nordisk**

Change in Weight	From baseline (week 0) to end of study*	kilogram (kg)
Change in Body Mass Index (BMI)	From baseline (week 0) to end of study*	kg/m 
Change in waist circumference	From baseline (week 0) to end of study*	cm
Change in waist-hip ratio	From baseline (week 0) to end of study*	ratio
Change in lipid profile (cholesterol, HDL, LDL, triglycerides)	From baseline (week 0) to end of study*	mg/dL
Change in HbA1C	From baseline (week 0) to end of study*	%
Change in bone density	From baseline (week 0) to end of study*	g/cm 
Change in bone mineral content	From baseline (week 0) to end of study*	g
Change in total body fat-mass	From baseline (week 0) to end of study*	kg
Change in truncal fat-mass	From baseline (week 0) to end of study*	kg
Change in lean body mass	From baseline (week 0) to end of study*	kg
Change in body fat percentage	From baseline (week 0) to end of study*	%
Change in visceral adipose tissue (VAT)	From baseline (week 0) to end of study*	cm 
Change in Liver function (AST, ALT, GGT, bilirubin)	From baseline (week 0) to end of study*	U/L
Change in PRO score, TRIM-AGHD	From baseline (week 0) to end of study*	-100 to +100
Patient reaching satisfactory clinical response	Approximately** 12 months after enrolment in study	Yes/No

\*End of study will differ from patient to patient, but can be between 1 week and a maximum of 10 years

\*\* i.e., the closest routine clinical after 12 months post enrolment

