#### **Continuous secondary endpoints:**

For the following secondary endpoints, the change will be estimated by length of follow-up and by treatment duration. Patients on oral oestrogen therapy and patients with childhood-onset GHD will be addressed in stratified analyses. The effect of a previous GH replacement therapy on the health-related quality of life will be checked in stratified analyses.

- Change in IGF-I SDS
- Change in weight
- Change in BMI
- Change in waist circumference
- Change in waist-hip ratio
- Change in lipid profile
- Change in HbA1C
- Change in bone density
- Change in bone mineral content
- Change in total body fat mass
- Change in truncal fat mass
- Change in lean body mass
- Change in body fat percentage
- Change in VAT
- Change in liver function
- Change in PRO score (TRIM-AGHD)

Protocol  
 Study ID: NN8640-4515  
 UTN: U1111-1264-8642  
 EU PAS No: Pending

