### 9.9 Limitations of the research methods

As this is a non-interventional study, data collection will reflect routine clinical practice rather than mandatory assessments at pre-specified time points, which may have an impact on the amount of data and its interpretation.

AGHD is characterised by low prevalence, resulting in the need to capture data from many different regions and settings. In addition to the non-interventional nature of the study, this leads to a potentially heterogeneous patient population and different local standard of care and data capture, e.g., local differences in diagnostics, laboratory analyses, and reporting of events. This could result in a risk of information bias.

In any non-interventional study, there is a risk of selection bias, affected by the willingness and/or ability of physicians and patients to participate in the study. In addition, any undiagnosed patients will not be able to participate, and the rate of underdiagnosis may vary between regions. This may lead to a selected patient population, which does not accurately reflect the underlying patient population and may result in limited data on certain subgroups.

The long-term follow-up is a strength of this non-interventional study, but also leads to a risk of loss to follow up.

As with any observational study, there is potential for bias resulting from variable quality and completeness in the information on potential confounders. Age, gender, previous GH treatment and medical history are among the potential confounders, and information on these will be collected to the extent possible. However, potential unmeasured confounding factors cannot be ruled out.

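### Triglyceride change is a secondary endpoint, but the only fasting preference is attached to the glucose samples and the protocol does not ask for fasting status, so fed and fasting lipid samples can be paired unseen

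*Protocol*

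**What the plan says.** - **Endpoint.** Protocol 9.1.1.2.2 lists "Change in lipid profile (cholesterol, HDL, LDL, triglycerides" among the clinical parameters, from baseline to end of study, in mg/dL.
- **Analysis.** Under 9.7.2.2, Continuous secondary endpoints, "the change will be estimated by length of follow-up and by treatment duration". The strata named in 9.7.2.2 include treatment-naïve versus prevalent GH users, oral oestrogen, childhood-onset GHD and baseline IGF-I. Fasting status is not among them.
- **Source of the samples.** Section 9.2.7.2: "Blood samples obtained from local laboratory in accordance with normal clinical practice should be recorded in the eCRF if available".
- **Fasting.** The same section says "Samples should preferably be obtained in a fasting state". The sentence stands under Glucose metabolism (insulin, blood glucose, HbA1c), after the lipid list has ended. It is the only mention of fasting in the protocol.
- **What must accompany the values.** "Applicable local laboratory reference ranges must be collected and shared with Novo Nordisk". Neither this section, the flow chart in 9.2.6.1 nor the other assessments in 9.2.8 list fasting status.
- **Baseline sample.** "Laboratory data obtained a maximum of 6 months before informed consent have been signed can be used for baseline data", provided the physician judges it still valid. Where several exist, the latest is used. Fasting state is not named as a criterion.
- **Design.** Section 9.1 describes a "prospective, single-treatment arm, observational PASS in AGHD patients".

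**The concern.** Triglycerides depend on recent food intake, so whether the patient had fasted is part of what the value measures. The protocol recognises that sampling state matters, but it attaches its one request to a group in which the only endpoint, HbA1c, is insensitive to it. The food-sensitive endpoint is left out.

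Two consequences are possible. Mixed sampling states add variation to each patient's change that has nothing to do with treatment. And if baseline samples are fasting more often, or less often, than routine follow-up samples, the mean change moves without any true change. The study has a single arm, so no concurrent control group would show the same artefact and allow it to be subtracted. The statistical analysis plan cannot repair this later: a status that was not captured at data entry cannot be used to separate the pairs.

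**Working it through.** The protocol states no figure on this point, so there is none to reproduce. The check has a text part and an illustration.

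**1. Text.** Set each analyte group in 9.2.7.2 against the endpoint list:

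| Group | Endpoint in it? | Depends on last meal? | Fasting preference? |
|---|---|---|---|
| Glucose metabolism | HbA1c only | HbA1c: no | yes |
| Lipid profile | all four lipids | triglycerides: yes | no |

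The preference covers no endpoint that needs it and omits one that does.

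**2. Illustration.** Let *m* be the fed-minus-fasting difference in triglycerides, and *f0* and *f1* the shares of fed samples at baseline and follow-up. None of these is in the documents. I assume *m* = 10 to 45 mg/dL, fed shares of 10% to 50% for the noise calculation, and a shift *f1 − f0* of 0 to 50 percentage points in either direction for the bias.

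*Bias in the mean change* = m × (f1 − f0):

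| m (mg/dL) | shift 0 | ±10 points | ±30 points | ±50 points |
|---|---|---|---|---|
| 10 | 0 | ±1.0 | ±3.0 | ±5.0 |
| 30 | 0 | ±3.0 | ±9.0 | ±15.0 |
| 45 | 0 | ±4.5 | ±13.5 | ±22.5 |

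The bias has the sign of the shift, and the documents do not indicate which sign that would be.

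*Noise.* If sampling state at the two visits is independent, the share of discordant pairs is f0(1 − f1) + f1(1 − f0). The component added to the SD of individual change is m × √[f0(1 − f0) + f1(1 − f1)].

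- f0 = f1 = 30%: discordant pairs 0.21 + 0.21 = 42%. Added SD = m × √0.42, which is 6.5 mg/dL at m = 10, 19.4 at m = 30 and 29.2 at m = 45.
- f0 = f1 = 50%: discordant pairs 0.25 + 0.25 = 50%. Added SD = m × √0.50, which is 7.1, 21.2 and 31.8 mg/dL.

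In both cases the bias in the mean is zero. The noise largely averages out: even at 31.8 mg/dL, with all 400 patients contributing a pair, this component alone gives a standard error of 31.8/√400 = 1.6 mg/dL. Fewer pairs would make it larger. A bias from a shifting fed share does not shrink with numbers.

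**3. After the change.** Among pairs recorded as fasting at both visits, f0 = f1 = 0, so both terms are zero to the extent that the recorded status is correct.

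**The case against.** The study collects only routine-practice data, so fasting cannot be imposed. Section 9.9 concedes that "data collection will reflect routine clinical practice rather than mandatory assessments at pre-specified time points", and it names local differences in laboratory analyses as a possible source of information bias. That covers this class of problem in general terms. It does not mention fasting, however, and conceding heterogeneity does not make it measurable. Recording the status imposes nothing on the patient. Section 9.2.8.3 already makes a comparable soft request for vital signs: the same method and position for each patient, if possible.

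It is also fair to say that no sentence here is wrong and no two sections conflict, that the choice of sample pairs for analysis normally belongs in the statistical analysis plan, and that triglycerides are one of four lipids within one of 16 continuous secondary endpoints. This limits the weight of the point. What remains is a preference placed with the wrong analyte group and a data item that later analysis cannot recover.

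A reader might go further and infer that fasting status will not be recorded at all, or that meal effects will be counted as change on treatment. The documents do not support either. The eCRF is not shown, so one can say only that the protocol does not ask for the item. Nothing in the protocol suggests that fasting practice differs between baseline and follow-up. The physician's validity judgement also places some limit on which earlier sample serves as baseline, although it is not a fasting rule.

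**Conclusion.** The point holds as a minor, inexpensive improvement. Fed and fasting triglyceride samples can be paired, and the data the protocol asks for would not show when this has happened. The certain part is textual: where the fasting sentence stands, and that no fasting status is requested. The size is conditional. Under the assumed meal effect of 10 to 45 mg/dL and a shift in fed share of up to 50 points, the spurious mean change lies between 0 and 22.5 mg/dL in absolute value. It is zero if the fed share is stable, and its direction is unknown otherwise. These are illustrations, not estimates. The conclusion is confined to the triglyceride part of the lipid endpoint. Blood glucose and insulin are not endpoints and already carry the preference. The primary endpoints and the sample size of 400, which rests on neoplasm incidence, do not change.

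**What to change.** - **Section 9.2.7.2:** extend the existing fasting preference to the lipid profile, still as a preference, and ask for fasting status (yes / no / unknown) with each lipid sample, taken from the medical record. This includes a baseline sample drawn before consent.
- **Analysis:** report change in triglycerides for all available pairs, with a supporting analysis by fasting status that shows pairs fasting at both visits. Keeping all pairs in the main report avoids making the endpoint depend on a subset that may over-represent sites or patients with fuller records.
- **Cost:** one sentence, one eCRF item per lipid sample and one supporting table, with no extra sample or procedure. Some entries will be unknown, and the supporting analysis will rest on fewer pairs.

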### 9.2.7.3 Physical examination

It is recommended to perform physical examination at every visit. The examination may include:

- Head, ears, eyes, nose, throat, neck
- Respiratory system
- Cardiovascular system
- Gastrointestinal system incl. mouth
- Musculoskeletal system
- Central and peripheral nervous system
- Skin
- Lymph node palpation

Results from physical examination should be recorded in the eCRF at baseline and at each visit throughout the study if available.

Data obtained a maximum of 6 months before informed consent has been signed can be used for baseline data if evaluated still to be valid by the physician. If data from more than one previously examination is available, the latest one should be used.

### 9.2.7.4 ECG

Results from ECG should be recorded in eCRF at baseline and at each visit throughout the study if available. ECG classified as abnormal and clinically significant at baseline should be recorded as medical history. Worsening of ECGs will be recorded as AE if they are evaluated as abnormal and clinically significant at a time after baseline.

Data obtained a maximum of 6 months before informed consent has been signed can be used for baseline data if evaluated still to be valid by the physician. If more than one previously obtained ECG is available, the latest one should be used.

Protocol  
Study ID: NN8640-4515  
UTN: U1111-1264-8642  
EU PAS No: Pending

CONFIDENTIAL

Date: 15 February 2022  
Version: 3.0  
Status: Final  
Page: 24 of 53

Novo Nordisk

### 9.2.7.5 Biomarkers

Samples obtained from local laboratory in accordance with normal clinical practice should be recorded in the eCRF if available:

- IGF-I
- IGFBP-3
- IGF-I standard deviation score (SDS)

Local Assay method and reference ranges must be collected and shared with Novo Nordisk.

Data obtained a maximum of 6 months before informed consent is signed can be used for baseline data if evaluated still to be valid by the physician. If more than one previously obtained data is available, the latest one should be used.

### 9.2.7.6 Body Composition

Results from body composition measurement by DXA or bioimpedance should be recorded in the eCRF at baseline and at each visit throughout the study if available.

Data obtained a maximum of 6 months before informed consent is signed can be used for baseline data if evaluated still to be valid by the physician. If more than one previously obtained data is available, the latest one should be used.

- Bone density
- Bone mineral content (hip or spine)
- Total body fat-mass
- Truncal fat mass
- Lean body mass
- Body fat percentage
- Visceral adipose tissue compartments (VAT)

## 9.2.8 Other assessments

### 9.2.8.1 Demography

Information about date of birth, sex, race, and ethnicity will be recorded in the eCRF according to local regulations.

### 9.2.8.2 Body Measurements

Height should be recorded in the eCRF at baseline only. Bodyweight, waist circumference and hip circumference should be recorded in the eCRF at all visits if available. Waste-hip ratio should be calculated and reported in eCRF at all visits if available.

For the baseline visit, height details in the medical records can be used, if evaluated as still relevant. For body weight, waist circumference and hip circumference data obtained a maximum of 6 months before signed informed consent can be used as baseline data, if evaluated as still relevant. For both men and woman, a waist hip ratio of 1.0 or higher is considered “at risk” for heart disease.

Protocol  
 Study ID: NN8640-4515  
 UTN: U1111-1264-8642  
 EU PAS No: Pending

**CONFIDENTIAL**

Date: 15 February 2022 **Novo Nordisk**  
 Version: 3.0  
 Status: Final  
 Page: 25 of 53

### **9.2.8.3 Vital Signs**

Blood pressure and pulse rate will be measured according to local clinical practice, preferably after the patient has rested comfortably for 3 minutes. Measurements of each individual patient should, if possible, be performed using the same method and position (e.g. sitting) throughout the study.

### **9.2.8.4 Tobacco use**

Information on tobacco use should be recorded in the eCRF at baseline and each visit throughout the study if available.

### **9.2.8.5 Concomitant illness**

Any clinically significant illness that is present at baseline will be recorded as concomitant illness. The information collected for concomitant illness will include diagnosis. In case a concomitant illness worsening during the study, an AE must be recorded and reported according to section [11](#).

### **9.2.8.6 Medical History**

The information collected for medical history should include diagnosis, date of resolution, as applicable and be recorded at the baseline visit based on discussion with the patient and/or based on medical records. In the event a diagnosis is unknown, the description of symptoms should be recorded.

At least history of cancer/intracranial tumour, history of GHD (childhood onset, adult onset, idiopathic, organic) should be recorded in the eCRF, if available.

To enable intra-personal comparison on dose of previous GH treatment, IGF-I/IGFBP-3 values, measures of body composition and bone health and oral oestrogen treatment status, 12 months of retrospective data (i.e., from medical charts, where available) will be collected at study enrolment. The severity of the GH deficiency (IGF-I level) from when the patient was GH treatment naïve should be collected as part of medical history, if available.

